Visit 3: Outcome Assessment Visit #2, Day 19 to 25 (14-20 days after completing the study agent). Subjects will be evaluated for the components of the composite overall outcome, which include the adequacy of the subject's clinical response; persistence of symptoms of fever, tachypnea, or cough; the occurrence of any solicited events; and the duration of antibiotic therapy (both study product/placebo and any additional oral or parenteral antibiotic therapy prescribed by study or non-study providers).

Subjects who are identified as having an inadequate clinical response prior to Outcome Assessment Visit #1 will be asked to complete Outcome Assessment Visits #1 and #2, in order to evaluate the occurrence of any solicited events and the duration of antibiotic therapy (both study product/placebo and any additional oral or parenteral antibiotic therapy prescribed by study or non-study providers).

Subjects will be invited to contribute oropharyngeal and stool specimens at specified times throughout the study for future use. Additional informed consent will be obtained for future use sample collection.

Figure 1: Schematic of the Study Design

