4.3.3. Reasons for Withdrawal

Subject Withdrawal

Subjects' parents/guardians may voluntarily withdraw their consent for study participation at any time and for any reason, without penalty.

A subject may withdraw or be withdrawn from the study for any of the following reasons:

- Withdrawal of consent
- Subject lost to follow-up
- Termination of the study
- Any new information becomes available that makes further participation unsafe.

Subjects who wish to withdraw from further study participation will be asked to continue to participate in follow-up visits. At the time of withdrawal, subjects will undergo an early termination visit, if they are not willing to participate in the remaining follow-up visits.

Discontinuation of Treatment

A subject may be discontinued from treatment and continue to be followed if any of individual halting rules (see Protocol) are met.

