6.5.1. Adequate Clinical Response to OAV#1 or OAV#2

Subjects that have no record of receipt of at least one dose of study product will have adequate clinical response and its components considered missing at both OAV#1 and OAV#2. Otherwise, if a subject dies at any point during subject participation in the study, the subject will be considered as not having adequate clinical response at OAV#1 or OAV#2. Otherwise, if a subject does not have OAV#1 then ACR and its components are missing for OAV#1 and if a subject does not have OAV#2 then ACR and its components are missing for OAV#2.

Several variables are used to define the Adequate Clinical Response:

- MAVABRX: Was the subject prescribed or did the subject receive an additional antibiotic treatment at this visit? (Yes/No)
 - o MAVABCP: If Yes, was the antibiotic given for pneumonia or treatment for a complication of pneumonia? (Yes/No)
- MAVPLEUR: Drainage of pleural fluid as treatment for pneumonia or a complication of pneumonia? (Yes/No)
- MAVCHTB: Placement of a chest tube as treatment for pneumonia or a complication of pneumonia? (Yes/No)
- MAVVIDEO: Video assisted thoracoscopic surgery as treatment for pneumonia or a complication of pneumonia? (Yes/No)
- MAVTHOR: Thoracotomy procedure as treatment for pneumonia or a complication of pneumonia? (Yes/No)
- MAVSURG: Any other surgical procedure as treatment for pneumonia or a complication of pneumonia? (Yes/No)
- MAVHOSP: Was the subject hospitalized at this visit? (Yes/No)
 - o MAVHPPN: If Yes, was the hospitalization for the treatment of pneumonia or pneumonia complications? (Yes/No)

If a subject has OAV#1 and did not have a medically attended visit (MAV) from Day 1 to Day 5, inclusive, then the subject had adequate clinical response for OAV#1. If the subject had a MAV from Day 1 to Day 5 for which MAVABRX and MAVABCP were both YES (receipt of a non-

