6.5.5. Ordinal Clinical Response at OAV#1 or OAV#2

If the subject died at any point of study participation, then OCR at OAV#1 will be 8.

Else if the subject has missing ACR at OAV#1 then OCR at OAV#1 will be missing.

Else if the subject did not have ACR at OAV#1 and was hospitalized from Day 1 to Day 5 then OCR at OAV#1 will be 7.

Else if the subject did not have ACR at OAV#1 and was not hospitalized from Day 1 to Day 5 then OCR at OAV#1 will be 6.

Else if the subject has missing resolution of symptoms at OAV#1 then OCR at OAV#1 will be missing.

Else if the subject did not have resolution of symptoms at OAV#1 then OCR at OAV#1 will be 5.

Else if the subject has missing most severe solicited event at OAV#1 then OCR at OAV#1 will be missing.

Else if the subject had a most severe solicited event of grade 3 at OAV#1 then OCR at OAV#1 will be 4.

Else if the subject had a most severe solicited event of grade 2 at OAV#1 then OCR at OAV#1 will be 3.

Else if the subject had a most severe solicited event of grade 1 at OAV#1 then OCR at OAV#1 will be 2.

Else OCR at OAV#1 will be 1.

If the subject died at any point of study participation, then OCR at OAV#2 will be 8.

Else if the subject has missing ACR at OAV#2 then OCR at OAV#2 will be missing.

Else if the subject did not have ACR at OAV#2 and was hospitalized from Day 1 to Day 18 then OCR at OAV#2 will be 7.

Else if the subject did not have ACR at OAV#2 and was not hospitalized from Day 1 to Day 18 then OCR at OAV#2 will be 6.

Else if the subject has missing resolution of symptoms at OAV#2 then OCR at OAV#2 will be missing.

Else if the subject did not have resolution of symptoms at OAV#2 then OCR at OAV#2 will be 5.

Else if the subject has missing most severe solicited event at OAV#2 then OCR at OAV#2 will be missing.

Else if the subject had a most severe solicited event of grade 3 at OAV#2 then OCR at OAV#2 will be 4.

Else if the subject had a most severe solicited event of grade 2 at OAV#2 then OCR at OAV#2 will be 3.

Else if the subject had a most severe solicited event of grade 1 at OAV#2 then OCR at OAV#2 will be 2.

Else OCR at OAV#2 will be 1.

Note that in some cases OCR can be defined even if some components are missing. For instance, if a subject had record of receipt of study product and did not have adequate clinical response at OAV#1, OCR at OAV#1 would still be defined even if most severe solicited event at OAV#1 was missing.

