6.6. Interim Analyses and Data Monitoring

One interim analysis, described below, will be performed by the SDCC statistician responsible for this protocol and reported to the DSMB after approximately 30% of the targeted subjects have completed the study. The interim analysis will inform DSMB decisions regarding stopping early for efficacy, futility, or safety. Only the SDCC statistician and the DSMB will see the interim analysis report.

For the interim analysis, a snapshot of the study database will be unblinded and used to conduct analyses as follows. An ITT analysis including all enrolled subjects in the snapshot of the study database will be performed, testing the null hypothesis (H_0 : Probability of higher DOOR in short course + $\frac{1}{2}$ probability of equal DOOR = 0.5) using the methods described in Section 8.1.1, with the modification that the Haybittle-Peto boundary ($p < 0.001$) will be used when concluding statistical significance. The study may be stopped early for efficacy only if statistical significance is detected in that test. In the event of statistical significance, sensitivity analyses using complete case and according-to-protocol cohorts (CC-V1 and ATP-V1, as described below) as well as worst case analyses will be included in the DSMB report to further guide decisions for stopping for efficacy.

A 95% confidence interval for the probability that a randomly selected subject will have a better DOOR if assigned to the 5-day strategy (vs. the standard strategy) will be estimated but not used to inform DSMB decisions about stopping early for efficacy. Predicted interval plots (PIPS, Section 6.6.1) will be constructed to provide the DSMB with a prediction of the trial results were the trial to continue as planned under varying assumptions regarding future data (e.g., current trend continues, null hypothesis is true, alternative hypothesis is true). In order to assess whether the 5-day strategy is differentially effective in subgroups of subjects, 95% confidence intervals for the probability of higher DOOR (as well as p-values for the test of a probability of higher DOOR of 0.5) when assigned to the short course of antibiotics will be shown as forest plots comparing each stratification variable (age < 2 years, age ≥ 2 years, ED as the initial treatment site, out-patient or urgent care as the initial treatment site, amoxicillin as the initial antibiotic, amoxicillin-clavulanate as initial antibiotic, and cefdinir as initial antibiotic).

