The DSMB will also be provided with the following:

1. For subjects that have completed Outcome Assessment Visit #1 and have received at least one dose of study product, a between arm difference in the overall outcome (DOOR) via a cumulative difference plot with respective confidence bands for Outcome Assessment Visit #1.
2. For subjects that have completed Outcome Assessment Visit #1 and have received at least one dose of study product, a forest plot of 95% confidence intervals for the risk difference of adequate clinical response as well as the following interventions for persistent or worsening pneumonia: (1) ED/clinic visits, (2) hospitalizations, (3) surgical procedures, and (4) non-study systemic antibiotics at Outcome Assessment Visit #1.
3. For subjects that have completed Outcome Assessment Visit #1 and have received at least one dose of study product, a forest plot of 95% confidence intervals for the risk difference of lack of resolution of symptoms as well as the following: (1) Oral, rectal, axillary or tympanic temperature $\geq 38.3^{\circ}\text{C}$ (100.9°F), confirmed by repeat measurement after at least 15 minutes, in the 24 hours preceding Outcome Assessment Visit #1 or measured at the assessment visit, unless attributed to a new process that is unrelated to the prior diagnosis of pneumonia; (2) Elevated respiratory rate (RR >50 breaths/minute for children <24 months of age and >40 breaths/minute for children 24-71 months of age) at Outcome Assessment Visit #1, and (3) Presence of cough Grade 2 or 3 at Outcome Assessment Visit #1.
4. For subjects that have completed Outcome Assessment Visit #1 and have received at least one dose of study product, a forest plot of 95% confidence intervals for the risk difference of each solicited event and with the risk difference of any solicited event, for each severity threshold (mild or greater, moderate or greater, or severe) for Outcome Assessment Visit #1.

The Newcombe method with continuity correction will be used to compute all 95% confidence intervals for risk differences.

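### The four numbered by-arm interim displays include only children who completed OAV#1, so deaths before that visit, and recorded Day 1-5 failures in children who never attend it, are left out

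*SAP*

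**What the plan says.** SAP 6.6 states the purpose of the interim report: "The interim analysis will inform DSMB decisions regarding stopping early for efficacy, futility, or safety". The report has two parts.

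The first is a test of the primary null hypothesis: "An ITT analysis including all enrolled subjects in the snapshot of the study database will be performed". With it come a confidence interval, predicted interval plots and subgroup forest plots. Complete-case, according-to-protocol and worst-case analyses follow only if the test is significant.

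The second is a list of four displays by arm. Item 1, the DOOR cumulative difference plot, begins "For subjects that have completed Outcome Assessment Visit #1 and have received at least one dose of study product, a between arm difference". Items 2 to 4 begin "For subjects that have completed Outcome Assessment Visit #1 and have received at least one dose of study product, a forest plot". They cover, in order, adequate clinical response (ACR) with its interventions for pneumonia, lack of symptom resolution, and solicited events. The protocol section Interim Analysis of Efficacy, Futility, and Safety has the same list and the same condition.

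Three other rules bear on this:

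- SAP 6.5.5 on death: "If the subject died at any point of study participation, then OCR at OAV#1 will be 8". No visit is needed.
- SAP 6.5.1 on a dosed survivor: "if a subject does not have OAV#1 then ACR and its components are missing for OAV#1".
- SAP 4.1 and 4.3.3 on attendance: "Subjects who are identified as having an inadequate clinical response prior to Outcome Assessment Visit #1 will be asked to complete Outcome Assessment Visits", but "At the time of withdrawal, subjects will undergo an early termination visit, if they are not willing to participate in the remaining follow-up visits".

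**The concern.** Whether a child completes OAV#1 can depend on how the child fared. A child who dies before Day 6 cannot complete it. A child who fails on Days 1-5 is referred to outside care, may come off study product, and may leave through an early termination visit. Selecting on completion can therefore remove the events that a safety reviewer most wants to see.

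Item 2 matters most, because no other pre-specified interim output shows pneumonia failure and hospitalization by arm. The main risk that the protocol names for short-course therapy (section 2.3.1) is a lower rate of adequate clinical response. A display that omits recorded failures is weakest on that question.

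**Working it through.** **Who is inside each interim output** (dosed children; SAP 6.5.1, 6.5.5, 6.5.6, 6.6)

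| Child | Items 1-4 | Interim ITT DOOR test |
|---|---|---|
| Failed on Days 1-5, attended OAV#1 | Included | Observed, OCR 6 or 7 |
| Died before OAV#1 | Absent | Observed, OCR 8 |
| Recorded failure or admission, survived, no OAV#1 | Absent | ACR set to missing, DOOR imputed |
| No recorded event, no OAV#1 | Absent | DOOR imputed |

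Row 2 conflicts with the SAP's own scoring. Death fixes OCR at 8, and SAP 6.5.6 supplies antibiotic days if they are missing, so DOOR is defined, yet the DOOR plot cannot contain the child. In row 3 the pseudocode of SAP 6.5.1 tests for a missing OAV#1 before it looks at any medically attended visit. A documented admission in a surviving non-attender is therefore also lost from the ITT test, where the value is imputed under missing at random.

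**The plan's figures.** Noether's formula in SAP 5, with p = 0.60 and equal allocation: (1.960 + 1.282)² / (12 × 0.25 × 0.10²) = 350.2, so 351 against the stated 360. Then 360 / 0.90 = 400. Both agree with the plan, and this point does not affect them. They supply the 10% used next.

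**Number outside the displays.** 30% of 400 is 120 children, about 60 per arm. 10% of 120 is 12, about 6 per arm.

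**Direction.** Let f be the true failure risk, and let d_f and d_n be the proportions of failing and other children without OAV#1.

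Displayed risk = f(1 − d_f) / [f(1 − d_f) + (1 − f)(1 − d_n)]

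This is below f whenever d_f exceeds d_n.

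**Size under assumptions.** The documents give neither failure risks nor selective loss. Assume f = 8% (short) and 3% (standard), and d_n = 8.7%. With d_f = 35%:

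- Short: 0.08 × 0.65 / (0.08 × 0.65 + 0.92 × 0.913) = 0.0520 / 0.8920 = 5.8%
- Standard: 0.03 × 0.65 / (0.03 × 0.65 + 0.97 × 0.913) = 0.0195 / 0.9051 = 2.2%

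Overall non-completion is then 10.8% and 9.5%, close to the planned 10%.

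| d_f | Displayed difference | Shortfall from 5.0 points | In children, at 60 per arm |
|---|---|---|---|
| 25% | 4.2 | 0.8 | 0.5 |
| 35% | 3.7 | 1.3 | 0.8 |
| 50% | 2.9 | 2.1 | 1.3 |

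**Precision.** SAP 6.6 specifies Newcombe intervals with continuity correction: from d − √[(p₁ − l₁)² + (u₂ − p₂)²] to d + √[(u₁ − p₁)² + (p₂ − l₂)²], where l and u are the Wilson limits. Assume 2 failures per arm among 54 completers. Then p = 3.7%, with limits 0.6% and 13.8%, and the display shows 0.0 points (−10.6 to 10.6) whatever happened to the 6 unseen children per arm. Now count all 60 per arm, with k recorded failures among the unseen short-course children and none in the standard arm:

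| k | Difference, short minus standard (95% CI), points |
|---|---|
| 0 | 0.0 (−9.6 to 9.6) |
| 1 | 1.7 (−8.3 to 11.9) |
| 3 | 5.0 (−5.6 to 16.1) |
| 6 | 10.0 (−1.6 to 22.1) |

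The last row is the extreme case. The displays as defined could not distinguish any of these rows from the others.

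**The case against.** Several stronger conclusions are tempting, and the documents do not support them.

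- *A reader might infer that every child hospitalized before OAV#1 drops out.* Children with inadequate response are asked to attend, and stopping study product is not study withdrawal (protocol 9.5.2). SAP 6.3 lists out-of-window or remote visits only as according-to-protocol exclusions, which suggests that they still count as OAV#1. A child is lost only if no OAV#1 is held.
- *A reader might infer that the filter could drive an efficacy stop.* It cannot. Such a stop requires significance in the ITT test on all enrolled children, which counts deaths in dosed children as OCR 8. A significant result also brings in the worst-case analysis, which generally scores missing short-course children as OCR 8.
- *A reader might infer that the DSMB would not learn of deaths.* Non-accidental death is a protocol-defined SAE, reported within 24 hours and reviewed by the medical monitor and the DSMB. The halting rules do not depend on OAV#1, and the DSMB may ask for more data.

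It is also fair to say that the size is assumed, that the shift is about one child or less in most of these scenarios against intervals of roughly ±10 points, and that children not yet due for OAV#1 must be kept out of a snapshot. The displays also resemble the final complete-case displays.

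What remains is a gap for failure and hospitalization that fall short of death. The halting rules (protocol 9.5.1) use trial-wide counts with no arm comparison. Their pneumonia criteria cover intensive-care or fatal admissions and failures within 3 days of starting study treatment. Protocol 9.3.1 keeps hospitalizations out of SAE reporting unless they meet the protocol-defined list, which does not name hospitalization. The worst-case analysis appears only after a significant test, so it may not be there when harm is the question. Similarity to the final analysis does not make a completer filter suitable for safety monitoring.

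**Conclusion.** The point holds in a limited form. All four numbered displays omit dosed children who died before OAV#1 and dosed children with a recorded Day 1-5 failure or admission who never attended. For failure and hospitalization, item 2 is the only pre-specified by-arm interim view.

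The size of the bias is unknown. If failing children attend less often, failure is understated. With the same attendance pattern in both arms, a short-course excess is also shrunk in the scenarios shown; if the pattern differs by arm, the difference could move either way. The 8% and 3% risks and the 25-50% selective loss are illustrations, not trial figures, and no changed DSMB decision has been shown. The sample size and the efficacy stopping rule are unaffected. The change is still worth making, because it is cheap and much of the omitted information is collected anyway.

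**What to change.** Amend SAP 6.6 and the matching protocol section as follows.

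- **Item 2.** Use all dosed children whose Day 1-5 window has elapsed, including those who died or left earlier. Count every recorded Day 1-5 failure, hospitalization, procedure, non-study antibiotic for pneumonia, and death, whether or not OAV#1 was held. State that, for this display, the rule in SAP 6.5.1 that sets ACR and its components to missing without OAV#1 does not override a recorded event. Without that sentence, a wider filter would only admit missing values.
- **Item 4.** Add solicited events recorded on Days 1-5 for children without OAV#1.
- **Item 1.** Keep the completer plot, and set beside it a companion version that adds deaths (OCR 8) and recorded failures (OCR 6 or 7). Other children without OAV#1 have no defined OCR, because symptom resolution is judged at the visit. The companion can therefore overstate failure and should be labelled as such.
- **Item 3.** Leave it restricted to attenders.
- **All items.** Show by arm the number without OAV#1, with reasons and known outcomes, so that children with no recorded event are not silently read as event-free.

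The sources exist: the health-record review before OAV#1 where possible (protocol 7.3), the early termination visit (Appendix A), and the telephone call about a week after withdrawal (protocol 5.3.4). The cost is a few sentences in each document and slightly more interim programming. The drawback is incomplete follow-up for some of the added children, which the by-arm counts make visible.

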6.6.1. Predicted Interval Plots (PIPs)

PIPs provide insight into the range of possible outcomes that can be expected for the final primary analysis under various assumptions (such as that the current observed treatment effect represents the true effect or that the null hypothesis represents the true effect). Using various assumptions, data is simulated from theoretical distributions to create multiple complete datasets representing complete datasets for the final analysis under the assumed reality. Details of PIPs and their interpretations can be found in the literature (Evans 2007, Li 2009).

For each assumption, one-hundred (100) 95% predicted intervals of the probability of higher DOOR in the 5-day treatment course at Outcome Assessment Visit #1 will be generated from 100 complete datasets. Each dataset will include the ITT analysis population for the interim analysis, plus additional simulated subjects to a total of 400 subjects in the dataset. Predicted intervals will be computed by inverting the Mann-Whitney U test (Section 8.2.2). The predicted intervals will be ordered by their corresponding point estimate of the probability of higher DOOR in the 5-day treatment course and shown graphically as forest plots. The 95% confidence interval generated in the ITT interim analysis of the probability of higher DOOR at Outcome Assessment Visit #1 will be overlaid on the forest plot. Comparisons of the predicted intervals to

the confidence interval show changes in precision of estimated probability (tightness of predicted intervals versus the confidence interval) as well as the expected distribution of location shifts of the estimated probability in the final analysis relative to the interim analysis, dependent on the assumptions used. Conditional power will be estimated as the percentage of predicted intervals with a lower bound that is greater than 0.5.

Three assumptions will be included in the PIPs: 1) current trend, 2) null hypothesis, and 3) alternative hypothesis. Further assumptions may be explored depending on results of the ITT analysis of the primary endpoint but will not be pre-specified.

Under the current trend assumption, each complete dataset is simulated in the following way. Multiple imputation will be used (Section 8.4.1) to create 100 datasets with complete data for DOOR at Outcome Assessment Visit #1 for enrolled subjects. For each of these 100 datasets, future subjects will be added to the analysis dataset. The number of future subjects added will be chosen to bring the total number of subjects (real and simulated combined) to 400 in the analysis dataset. The treatment ratio in the simulated subjects will be 1:1. The DOOR values for the future subjects in each dataset will be simulated by sampling with replacement from the empirical distribution of DOOR values by treatment from the same dataset.

Under the null hypothesis assumption, each complete dataset is simulated in the following way. Multiple imputation will be used (Section 8.4.1) to create 100 datasets with complete data for DOOR at Outcome Assessment Visit #1 for enrolled subjects. For each of these 100 datasets, future subjects will be added to the analysis dataset. The number of future subjects added will be chosen to bring the total number of subjects (real and simulated combined) to 400 in the analysis dataset. The treatment ratio in the simulated subjects will be 1:1. The DOOR values for the future subjects in each dataset will be simulated by sampling with replacement from the overall (not by treatment) empirical distribution of DOOR values from the same dataset.

Under the alternative hypothesis assumption, each complete dataset is simulated in the following way. Multiple imputation will be used (Section 8.4.1) to create 100 datasets with complete data for DOOR at Outcome Assessment Visit #1 for enrolled subjects. For each of these 100 datasets, future subjects will be added to the analysis dataset. The number of future subjects added will be chosen to bring the total number of subjects (real and simulated combined) to 400 in the analysis dataset. The treatment ratio in the simulated subjects will be 1:1. The DOOR values for the future subjects in each dataset will be simulated by sampling with replacement from the overall (not by treatment) empirical distribution of DOOR values from the same dataset. All simulated subjects with a treatment assignment randomly chosen as the 5-day course will have the DOOR (rank) shifted by a value β . The value β will be chosen through a manual trial-and-error process such that the probability of higher DOOR in the 5-day subjects, comparing simulated subjects only, has a mean value of approximately 0.6 across all 100 datasets.

